7.3. Exploratory Efficacy Analyses

Moderate/severe asthma exacerbations will be summarized, including number of subjects with moderate/severe exacerbations, number of moderate/severe exacerbations and characteristics of moderate/severe exacerbations. Exacerbations separated by less than 7 days will be treated as a continuation of the same exacerbation

The moderate/severe exacerbation rate will be analyzed using a generalized linear model, assuming the number of exacerbations has a negative binomial probability distribution and that its mean is related to covariate factors with a 'log link' function. The logarithm of time (year) on study will be used as an offset variable. All moderate/severe

exacerbations observed during the study, with the onset date of event from date of baseline visit to the end of study visit date or early withdrawal (from study) visit date, will be included in the analysis. Missing data due to early withdrawal from the study will not be imputed. The model will include covariates for treatment, baseline ACT total score, type of baseline controller (ICS alone vs. ICS/LABA), gender and age. The annual moderate/severe exacerbation rates and 95% confidence interval for each treatment will be presented. The rate ratio and 95% confidence interval, percent reduction in rate and 95% confidence interval and P value will also be presented.

The example SAS codes are as below:

```
proc genmod data= input_data;  
  class rndgrp blcontrol gender;  
  model no_exac = rndgrp actbl blcontrol gender age / dist=negbin  
link=log offset=logtime wald type3;  
  lsmeans rndgrp / cl diff OM exp;  
run;
```

where input_data is the name of the input dataset and no_exac is the number of moderate/severe asthma exacerbations per subject during the study. In terms of the covariates rndgrp, actbl, blcontrol, gender and age are variables for randomised treatment code, baseline ACT total score, type of baseline controller, gender and age respectively. For offset, logtime is logarithm of time (year) on study.

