4.2. Treatment Arms and Duration

- The study is planned to be a 24-week study.
- Baseline (week 0, visit 0): Subjects eligible for inclusion criteria will sign informed consent form at Visit 0. At this visit, investigators should collect baseline data, including demographic data (gender, age, height, weight, education level and smoking history), history of asthma (disease duration, disease severity and exacerbation history), and past and concurrent medical conditions and medication (both asthma and non-asthma). ACT, AQLQ(S) and lung function test will be completed as the baseline measurement in sequence.
- Treatment period (week 0-week 24): a 24 week treatment period. Subsequent scheduled visits occur as follows: Week 4 (Visit 1), Week 8 (Visit 2), Week 12 (Visit 3), Week 16 (Visit 4), Week 20 (Visit 5) and Week 24 (Visit 6).
- In this cluster-randomization design, each study centre, considered as a cluster, will be randomized to either ACT guided treatment group or control group (usual care group). The randomization will be stratified according to the hospital level (Tier 3 vs. Tier 2). The hospital level is determined in accordance with the uniform requirements of the government. And a Tier 3 hospital is on a larger scale and provides superior medical care than a Tier 2 hospital.
- For the subjects who are recruited in the ACT centres, they will be treated based on the ACT score. For subjects who are recruited in the control centres, they will be treated based on doctor's subjective judgment.

Table 1 ACT-guided treatment

ACT score	Treatment adjustment
ACT=25, ≥ 3 months	Step-down treatment
ACT ≥ 20 , <25 or ACT=25, <3 months	No change

ACT score	Treatment adjustment
ACT \leq 19	Step-up treatment

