5.2. Exclusion Criteria

A subject will not be eligible for inclusion in this study if any of the following criteria apply:

1. History of Life-threatening asthma: Defined for this protocol as an asthma episode that required intubation and/or was associated with hypercapnea, respiratory arrest or hypoxic seizures within the last 6 months before Visit 0.
2. Subjects having severe and unstable asthma, with ACT score <12 at Visit 0, history of repeated severe exacerbations (3/year) and/or a severe exacerbation in the previous 6 weeks before Visit 0.
3. A current evidence of clinically significant uncontrolled medical condition or disease (e.g., psychological disorders, mental deficiency, severe hepatic and renal dysfunction, malignancy);
4. Current smoker or ex-smoker with a more than 10 pack-year history of smoking;
5. Current clinically significant respiratory diseases other than asthma, (e.g lung cancer, lung fibrosis, sarcoidosis, tuberculosis, chronic obstructive pulmonary disease [COPD]);
6. History of alcohol or medication abuse;
7. History of upper or lower respiratory tract infection within 4 weeks prior to Visit 0;
8. Enrolled in an asthma clinic or outpatient service in the past 12 months that provides comprehensive asthma management;
9. Subjects with a history of adverse reaction including immediate or delayed hypersensitivity to any intranasal, inhaled, or systemic corticosteroid and LABA therapy and to components of the inhalation powder (e.g., lactose) at Visit 0. In addition, subjects with a history of severe milk protein allergy that, in the opinion of the Investigator, contraindicates the subject's participation will also be excluded.
10. Females who are currently pregnant and lactating;
11. Subjects who have received any of the following medications in the 6 weeks preceding visit 0: oral/parenteral corticosteroids, oral β 2-agonists or slow-release

bronchodilators, sodium cromoglycate or nedocromil sodium, ketotifen, anticholinergics, and anti-IgE treatment;

12. Subjects who comply poorly with asthma treatment in the opinion of the investigator/inability or unwillingness to take asthma medication (non-compliance), follow directions or unable to complete a written paper daily record card and self-rating questionnaires;

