7.2. Screening and Critical Baseline Assessments

Baseline Assessments	
Demographic information	Gender ethnic origin date of birth, height weight education level smoking history
History of asthma including duration of asthma	
History of asthma exacerbations in the 12 months prior to Visit 0	
Concurrent medical conditions and concurrent medication	
Medical history	Use of corticosteroids for asthma in the 12 months prior to Visit 0 duration of inhaled corticosteroid treatment

The following demographic parameters will be captured: year of birth, sex, race and ethnicity.

Medical/medication will be assessed as related to the inclusion/exclusion criteria listed in Section 5.

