6. STUDY POPULATION ANALYSES

6.1. Overview of Planned Study Population Analyses

The study population analyses will be based on the ITT population, unless otherwise specified.

Study population analyses including analyses of subject's disposition, population, protocol deviations, demographic and baseline characteristics, subject's smoking history, alcoholism history, drug abuse history, asthma history, asthma exacerbation history, medical history (coded by MedDRA version 21.0 or above), asthma medications, and concomitant medications (coded by WHODrug version Global Mar 2018 or above), will be summarized and listed. Details of the planned displays are presented in [Appendix 8: List of Data Displays](#).

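### The SAP's exacerbation-rate model omits the collected 12-month exacerbation history, so an arm difference in prior risk that the other covariates do not explain passes into the rate ratio

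*SAP*

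**What the plan says.** SAP section 7.3 models the number of moderate/severe exacerbations per subject with a negative binomial distribution and a log link. On follow-up time it says: "The logarithm of time (year) on study will be used as an offset variable". On covariates it says: "The model will include covariates for treatment, baseline ACT total score, type of baseline controller (ICS alone vs. ICS/LABA), gender and age". The example code agrees with the text: "model no_exac = rndgrp actbl blcontrol gender age / dist=negbin". Neither has a term for earlier exacerbations.

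The variable exists. Protocol section 7.2 lists "History of asthma exacerbations in the 12 months prior to Visit 0" among the baseline assessments, and Protocol section 4.2 also names exacerbation history in the Visit 0 data. The SAP's only use for it is in section 6.1, where "asthma exacerbation history" is one of the items to be summarised and listed. The sensitivity and supportive analyses in SAP section 7.1.3 all concern ACT, and section 7.3 has none for this endpoint.

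Eligibility narrows the range of history. Exclusion criterion 2 in Protocol section 5.2 names "history of repeated severe exacerbations (3/year) and/or a severe exacerbation in the previous 6 weeks before Visit 0". Criterion 11 excludes oral or parenteral corticosteroids in the 6 weeks before Visit 0. Protocol section 7.3.3 defines a moderate exacerbation by oral corticosteroid treatment, so recent moderate events are largely excluded as well. Moderate events between 6 weeks and 12 months before entry, and infrequent severe ones in that window, remain eligible.

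**The concern.** A subject's past exacerbations are the natural baseline for a model of future exacerbations. The SAP follows that principle elsewhere: baseline ACT score enters the primary model and the model for change in ACT. In section 7.3 the exacerbation model also gets baseline ACT, but not baseline exacerbations. ACT has a four-week recall period (Protocol section 7.3.1), so it is not a substitute for a 12-month history.

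Imbalance is plausible. Only 12 centres are randomised, six per arm, and hospital tier is the only stratum. The study is open label, so staff can know their centre's arm when they recruit. Protocol section 6.1 asks for consecutive patients, but exclusion criterion 12 rests partly on investigator opinion.

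What is at stake is the rate ratio, percent reduction, confidence interval and p-value that SAP section 7.3 commits to report. If the baseline table shows an imbalance, the plan has no prespecified response, and any adjustment would be a post hoc choice.

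**Working it through.** **Figures the plan gives.** None for this endpoint: no exacerbation rate, dispersion, ICC or power. Protocol section 9.2.1 supplies the trial's size, which reproduces for the primary endpoint:
- Design effect: 1 + (35 − 1) × 0.01 = 1.34.
- Effective size per arm: 210 / 1.34 = 156.7. With 29% vs 44% this gives 79.0% power, against 80% stated.
- Enrolment: 35 / 0.80 = 43.75, so 44 per centre, and 44 × 12 = 528.

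**Step 1: chance imbalance.** With m subjects per centre and six centres per arm, the SD of the arm difference in mean prior count is √(2 × var × (1 + (m − 1) × ICC) / (6m)). Multiplying by the log rate ratio per prior event and exponentiating gives the shift in the unadjusted rate ratio. Assumed: m = 35, mean prior count 0.3 to 1.0, var = mean + mean² (dispersion 1), ICC 0.01 to 0.10, rate ratio per prior event 1.5 to 2.0.

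Example with mean 0.5 and ICC 0.01: var = 0.75, and √(2 × 0.75 × 1.34 / 210) = 0.098. At a ratio of 1.5 per event, exp(0.098 × 0.405) = 1.04. At 2.0, exp(0.098 × 0.693) = 1.07.

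| Mean, ICC | Shift at 1 SD | Shift at 1.96 SD |
|---|---|---|
| 0.3, 0.01 | 1.03 to 1.05 | 1.06 to 1.10 |
| 0.5, 0.01 | 1.04 to 1.07 | 1.08 to 1.14 |
| 1.0, 0.10 | 1.13 to 1.22 | 1.26 to 1.48 |

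**Step 2: does baseline ACT absorb it?** A null simulation (mean prior count 0.5, baseline ACT correlated with history and included in both models) compared the fits with and without history. Adding history changed the log rate ratio by an SD of 0.06 to 0.22. The change was 0.55 to 1.25 per one-event arm difference, against true log effects of 0.41 to 0.69. In these settings ACT did not absorb the imbalance. The mean log rate ratio over repeated randomisations lay between −0.02 and 0.02 in both models, so there was no expected bias. Dispersion was held fixed and the other covariates had no effect.

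**Step 3: selective recruitment.** Null simulations used 528 subjects, rate 0.7 per year and dispersion 2. The arms differed in the share with any prior exacerbation by 31–33% vs 39%. Share of log bias removed = 1 − |ln RR with history| / |ln RR without|; for example, 1 − 0.139 / 0.211 = 34% for 0.81 → 0.87.

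| Selection acts on | Correlation of prior and on-study risk | Mean RR without → with history | Removed |
|---|---|---|---|
| Underlying risk, all events | 0.5 / 0.7 / 0.9 | 0.85→0.90 / 0.81→0.87 / 0.75→0.84 | 35% / 34% / 39% |
| Underlying risk, first event only | 0.5 / 0.7 / 0.9 | 0.88→0.92 / 0.81→0.87 / 0.76→0.83 | 35% / 34% / 32% |
| Underlying risk, separate run | 0.7 / 0.9 | 0.83→0.89 / 0.79→0.87 | 37% / 41% |
| Recorded history | 0.7 / 0.9 | 0.954→1.018 / 0.921→1.007 | 62% / 92% |

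Each figure is a mean over 250 to 400 trials. If the SD of the log rate ratio is 0.24 to 0.32, as in Step 2, Monte Carlo error is about 0.24/√400 = 0.012 to 0.32/√250 = 0.020.

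**Step 4: precision.** At a true rate ratio of 0.6 with all events counted (control rate 0.5 or 1.0 per year, dispersion 1 or 3, correlation 0.5 to 0.9), the history term raised power by 0 to 6.7 points. The extremes were 85.8% → 85.8% and 73.8% → 80.5%. Variance of the log rate ratio fell by about 0 to 20%, and by 22% in one run with between-centre variation. When follow-up stopped at the first event, the gain was about 3 points and the variance ratio was 0.99 to 1.14.

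**The case against.** The strongest case on the other side is that this is a preference about a covariate in an exploratory model. Every size is assumed, expected bias under fair randomisation is nil, and history is displayed by SAP section 6.1, so an imbalance would be visible. All of that is right. It limits the weight of the point but does not answer it, because seeing an imbalance does not say how to handle it.

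Three stronger readings are tempting, and the documents do not support them:
- **A reader might infer that any arm difference in prior risk enters the rate ratio.** Only the part not explained by baseline ACT, controller type, gender and age does.
- **A reader might infer that the history term cures the problem.** A recalled or recorded history measures risk with noise. When selection acts on underlying risk, about a third of the bias goes.
- **A reader might infer that adjustment cannot cost precision.** Protocol section 5.3 lists a protocol-defined exacerbation as a reason for discontinuation. SAP section 7.3 counts exacerbations per subject, and Protocol section 7.3.3 has a rule for separating successive courses. These passages must be reconciled. If follow-up ends at a first event, variance can rise by up to 14%, although the reduction in bias persists.

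One further objection stands. The documents say that history is collected but not that it is a count, nor that the on-study moderate/severe definition is applied to the past year.

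**Conclusion.** The omission is confirmed in both text and code, and it concerns a variable the trial already collects. Residual imbalance in prior exacerbation risk will pass into the rate ratio. This is chance imbalance unless recruitment is selective, and nothing in the documents shows that it is. Under the assumptions above, chance imbalance shifts the ratio by a factor of 1.03 to 1.22 at 1 SD and 1.06 to 1.48 at 1.96 SD; a mid-range setting (mean 0.5, ICC 0.01) gives 1.04 to 1.07 and 1.08 to 1.14. Adjustment reduces the distortion, partly or mostly according to its source. Protection against imbalance is the reason to adjust, since the power gain is minor. This is a minor improvement with no bearing on the primary analysis.

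**What to change.** Before database lock, add exacerbation history in the 12 months before Visit 0 to the covariate list in SAP section 7.3. Code it as 0, 1, 2 or more if the CRF records a count, and otherwise as any versus none. In the example code, add the variable (say `exachist`) to the CLASS statement and to the right-hand side of the MODEL statement. Keep the current model as a sensitivity analysis.

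The cost is one or two degrees of freedom and reliance on a recalled or recorded history. No new data are needed if the CRF field supports the coding, so check that first. This change does not settle a separate matter: SAP section 7 says analysis models adjust for centre, and the section 7.3 model has no centre term.

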8. SAFETY ANALYSES

The safety analyses will be based on the Safety population, unless otherwise specified.

8.1. Adverse Events Analyses

The number (%) of subjects in each treatment group with treatment emergent AEs will be produced. Counts and percentages will also be presented of subjects with serious adverse events (SAEs), AEs leading to withdrawal, AEs by severity, AEs by relationship to study procedure/study drug, asthma exacerbation and death.

Adverse events will be coded by MedDRA version 21.0 or above. Adverse events will be summarized and presented by system organ class (SOC) and preferred term (PT) by treatment group. Adverse events analyses including the analysis of AEs, SAEs, non-serious AE and other significant AEs will be summarized. All AEs and SAEs will be listed. The details of the planned displays are provided in [Appendix 8: List of Data Displays](#).

8.2. Adverse Events of Special Interest Analyses

Except for study indication Asthma, there is no other adverse event of special interest.

8.3. Clinical Laboratory Analyses

Clinical laboratory data is not collected and analysed in this study.

8.4. Other Safety Analyses

The analyses of non-laboratory safety test results including vital signs and physical examination will be summarized and listed by descriptive statistics. The details of the planned displays are presented in [Appendix 8 List of Data Displays](#).

10. APPENDICES

**10.1. Appendix 1: Protocol Deviation Management and Definitions
for Per Protocol Population**

Refer document “PDMP201097 final.docx”

10.2. Appendix 2: Schedule of Activities

10.2.1. Protocol Defined Schedule of Events

ACTIVITY	Visit 0	Visit 1	Visit 2	Visit 3	Visit 4	Visit 5	Visit 6 (or Early Withdrawal)
Study Week (Visit Window)	0	4w± 1	8w± 1	12w± 1	16w± 1	20w± 1	24w± 1
Informed consent	x						
Randomization/Allocation of clusters	x						
Subject Demography	x						
Medical history	x						
Verification of inclusion/exclusion criteria	x						
Efficacy Evaluation							
Verification of withdrawal criteria		x	x	x	x	x	x
Issue diary record cards	x	x	x	x	x	x	
Collect/Review diary record cards		x	x	x	x	x	x
Compliance assessment		x	x	x	x	x	x
Asthma control Test (ACT) score	x	x	x	x	x	x	x
AQLQ(S)	x						x
Lung function Test	x						x
Safety Evaluation							
Adverse event assessment ¹	x	x	x	x	x	x	x

1. Serious AEs will be recorded from the time the consent form is signed until the follow-up visit. All AEs will be recorded from the start of study treatment until the follow-up visit.

10.3. Appendix 3: Study Phases and Treatment Emergent Adverse Events

Assessments and events will not be classified by study phase. All the adverse events and concomitant medications are collected during the study as treatment emergent adverse events.

10.4. Appendix 4: Derived and Transformed Data

10.4.1. General

Multiple Measurements at One Analysis Time Point

• Mean of the measurements will be calculated and used in any derivation of summary statistics but if listed, all data will be presented.• Participants having both High and Low values for Normal Ranges at any post-baseline visit for safety parameters will be counted in both the High and Low categories of “Any visit post-baseline” row of related summary tables. This will also be applicable to relevant Potential Clinical Importance summary tables.
Study Day

• Not Applicable.

10.5. Appendix 5: Reporting Standards for Missing Data

10.5.1. Premature Withdrawals

Element	Reporting Detail
General	
 • Subject study completion (i.e. as specified in the protocol) was defined as who has completed all visits of the study. • Withdrawn subjects were not replaced in the study. • All available data from participants who were withdrawn from the study will be listed and all available planned data will be included in summary tables and figures, unless otherwise specified. • Withdrawal visits will be slotted as per Appendix 2: Schedule of Activities or will be summarised as withdrawal visits.

10.5.2. Handling of Missing Data

Element	Reporting Detail
General	
 • Missing data occurs when any requested data is not provided, leading to blank fields on the collection instrument: 
 • These data will be indicated by the use of a “blank” in subject listing displays. Unless all data for a specific visit are missing in which case the data is excluded from the table. • Answers such as “Not applicable” and “Not evaluable” are not considered to be missing data and should be displayed as such.
Outliers	
 • Any participants excluded from the summaries and/or statistical analyses will be documented along with the reason for exclusion in the clinical study report.

10.5.2.1. Handling of Missing and Partial Dates

Element	Reporting Detail
General	
 • Partial dates will be displayed as captured in subject listing displays.
Adverse Events	
 • Completely missing start or end dates will remain missing, with no imputation applied. • Also no imputation applied for Partial dates. • The recorded partial date will be displayed in listings.
Concomitant Medications/ Medical History	
 • Completely missing start or end dates will remain missing, with no imputation applied. • Also no imputation applied for Partial dates. • The recorded partial date will be displayed in listings.

10.6. Appendix 6: Values of Potential Clinical Importance

10.6.1. Laboratory Values

Laboratory values are not collected in this study.

10.6.2. ECG

ECG values are not collected in this study.

10.6.3. Vital Signs

Vital Signs Values are only collected at Visit 0 as baseline characteristics, will be listed and summarized by descriptive statistics, normal range and clinical concern range will not be collected and summarized.

10.7. Appendix 7: Abbreviations & Trade Marks

10.7.1. Abbreviations

Abbreviation	Description
ACT	Asthma Control Test
AE	Adverse Event
ANCOVA	Analysis of Covariance
AQLQ	Asthma Quality of Life Questionnaire
AQLQ(S)	Standardised Asthma Quality of Life Questionnaire
CRF	Case Report Form
DRC	Daily Record Card
ECG	Electrocardiogram
FEV1	Forced Expiratory Volume in one second
GINA	International Guidelines for Asthma Management
GSK	GlaxoSmithKline
ITT	Intention-to-Treat
LABA	Long-acting β 2 agonist
MedDRA	Medical Dictionary for Regulatory Activities
Mg	Milligram/s
mL	Millilitre/s
PEF	Peak Expiratory Flow
PP	Per Protocol
PT	Preferred Term
RAP	Reporting and Analysis Plan
SAE	Serious Adverse Event
SOC	System Organ Class
SD	Standard Deviation

Abbreviation	Description
WHO	World Health Organisation

10.7.2. Trademarks

Trademarks of the GlaxoSmithKline Group of Companies
ACT

Trademarks not owned by the GlaxoSmithKline Group of Companies
AQLQ(S)
MedDRA
SAS
WHODrug

10.8. Appendix 8: List of Data Displays

10.8.1. Data Display Numbering

The following numbering will be applied for RAP generated displays:

Section	Tables	Figures	Listings
Study Population	1.01 to 1.09		1.01 to 1.10
Efficacy	2.01 to 2.28	16	2.01 to 2.04
Safety	3.01 to 3.11		3.01 to 3.03

For Details of Mock Shells for Data Displays, please refer document “C_012_RESP_201097_TFL Template_Mock-ups.doc”.
